### Sample SAS Code for GEE

```
proc gee data=data;
  class trtp(ref="Placebo") avisit usubjid;
  model avalc = trtp avisit trtp*avisit base / dist=binomial link=logit;
  repeated subject= usubjid / corrb corrw covb type=UN;
  lsmeans trtp*avisit / diff oddsratio cl;
  ods output diffs=diffs responseprofile=proportion;
run;
```

### Sample SAS Code for PMM-MI under MNAR

#### Step 1. Assessing the pattern of missing data

```
proc mi data=non_mono seed=xxx n impute=0;
  var trtp base y1-y3; *y1=Day 14, y2=Day 28, y3=Day 84;
  ods output misspattern=pattern;
run;
```

#### Step 2. Turning the arbitrary missing patterns to monotone missing patterns under MAR assumption

```
proc mi data=non_mono out=mono seed=xxx n impute=m;
  min=.. x x x; *period (.) means no imputation needed;
  max=.. y y y;
  var trtp base y1 y2 y3;
  mcmc chain=multiple impute=monotone;
run;
```

#### Step 3. Generation of imputed datasets for AVAL using control-based pattern imputation under MNAR

```
proc mi data=mono seed=xxx n impute=m outs=imputed;
  min=.. x x x;
  max=.. y y y;
```

```
by _imputation_;  
class trtp;  
var y1 y2 y3;  
monotone reg(/details);  
mnar model(y1 y2 y3/ modelobs=(trtp='Placebo')); *only control group is used to  
derive the imputation model;  
run;
```

Step 4-1. Calculate CHG14, CHG28, and CHG84.

Step 4-2. Convert datasets into long format in which CHG variable represents all change  
from baseline with different values of avisit.

Step 5. Conducting model-based analysis using each imputed dataset

```
proc mixed data= imputed;  
by _imputation_;  
class subjid trtp(ref='Placebo') avisitn;  
model chg = trtp base avisitn trtp*avisitn / ddfm=kenwardroger;  
repeated avisitn / subject=usubjid type=UN;  
lsmeans trtp*avisitn / diff=all cl alpha=0.05;  
ods output lsmeans=lsmeans diff=diffs;  
run;
```

Step 6. Pooling the results from the imputed *m* datasets for inference

```
proc sort data=lsmeans;  
by trtp avisitn _imputatoin_;  
run;  
  
proc mianalyze parms=lsmeans;  
modeleffects estimate;  
ods output ParameterEstimates=lms;  
by treatment avisit;  
run;
```

```
proc sort data=diffs;  
by avisit _imputatoin_;  
run;  
  
proc mianalyze parms=diffs;  
modeleffects estimate;  
ods output ParameterEstimates=dif;  
by avisit;  
run;
```

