- 5) The population summary level deals with the difference between SAGE-718 and placebo treatments in mean change from baseline to Day 84 in Symbol Digit Modalities Test (SDMT) The primary efficacy endpoint is the change from baseline to Day 84 on the SDMT score. This primary endpoint will be analyzed using a mixed-effects model for repeated measures (MMRM). The model will include baseline SDMT score as a continuous explanatory variable, treatment, assessment time point, and time point-by-treatment as categorical explanatory variables. The Kenward-Roger correction to degrees of freedom will be applied. All explanatory variables will be treated as fixed effects in the model. All post-baseline time points will be included in the model. An unstructured (UN) covariance matrix with the default Newton-Raphson optimization algorithm as implemented in the SAS procedure PROC MIXED will be used to estimate the within-subject correlation. If this model fails to converge, the Fisher Scoring algorithm (via the SCORING option of the PROC MIXED statement), the no-diagonal factor analytic structure (via the TYPE=FA0( $T$ ) option of the REPEATED statement, where  $T$  is the total number of time points), Toeplitz, Autoregressive (1) [AR (1)], Compound symmetry (CS) covariance structure will be used, following this sequence until convergence is achieved. If the model still does not converge with CS structure, the Glimmix procedure with option of parametrizing UN to Cholesky root matrix will be used and in the case it also does not converge no results will be reported. When the covariance structure is not UN, the sandwich estimator for the variance-covariance matrix will be derived, using the EMPIRICAL option in the PROC MIXED statement in SAS. The primary comparison will be between SAGE-718 and placebo at the Day 84. Least squares means and 95% confidence interval will be summarized, and the p-value from the hypothesis test of no difference between the treatment groups will be also presented.

A plot showing the LS means of SDMT score  $\pm$  SE bar over time within each treatment group will be provided.

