### 8.3.3.2. Sensitivity Analysis of Primary Endpoint

Sensitivity analysis is planned if >5% of participants in any treatment group have missing data in the primary endpoint or the values could not be used due to the use of prohibited medications.

If any of the sensitivity analyses yields a result that is in a different direction from the result of the primary analysis, the nature of the discrepancy will be examined to clearly explain the discrepancy based on statistical principles and the discrepancy will be discussed in the CSR.

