### 8.3.3.3. Supportive Analysis of Primary Endpoint

The primary analysis will be repeated based on the █. No sensitivity analysis will be performed based on the █.

A forest plot of the difference in LS means and 95% CI bar for the changes from baseline to Day 84 on SDMT score using primary analysis, sensitivity analyses (excluding tipping point analysis) and supportive analysis will be provided.

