### **Sample SAS Code for Tipping Point Analysis**

```
/*-----*/
```

```
/*--- Generate imputed data set for specified shift parameters ---*/
/*--- data= input data set ---*/
/*--- smin= min shift parameter ---*/
/*--- smax= max shift parameter ---*/
/*--- sinc= increment of the shift parameter ---*/
/*--- out= output imputed data set ---*/
/*-----*/
%macro midata( data=, smin=, smax=, sinc=, out=);
  data &out;
  set _null_;
run;

/*----- # of shift values -----*/
%let ncase= %sysevalf( (&smax-&smin)/&sinc, ceil );
/*----- Imputed data for each shift -----*/
%do jc=0 %to &ncase;
  %let sj= %sysevalf( &smin + &jc * &sinc);
  proc mi data=&data seed=xxx nimpute=m out=outmi;
    class trtp;
    monotone reg(y1 y2 y3);
    mnar adjust( y1 y2 y3 / shift=&sj adjustobs=(trtp='Placebo') ); *active treatment is
    used;
    var trtp y1 y2 y3;
  run;

  data outmi;
    set outmi;
    Shift= &sj;
  run;

  data &out;
    set &out outmi;
  run;
%end;
%mend midata;
```

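### Step 3 of the control-based imputation sample code leaves out baseline SDMT, so this sensitivity estimate can shift modestly when selective dropout differs between arms

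*SAP*

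**What the plan says.** SAP Section 8.3.3.2.2 describes a control-based pattern mixture imputation for the primary endpoint but lists no imputation covariates. The variables appear only in the sample code of SAP Appendix B:

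- Step 1 (missing-data pattern): "var trtp base y1-y3; *y1=Day 14, y2=Day 28, y3=Day 84".
- Step 2 (conversion to a monotone pattern): "var trtp base y1 y2 y3".
- Step 3 (the control-based imputation): "var y1 y2 y3; monotone reg(/details); mnar model(y1 y2 y3/ modelobs=(trtp='Placebo". It imputes the raw score; change from baseline is derived afterwards, in Step 4-1.
- Step 5 (analysis of each imputed dataset): "model chg = trtp base avisitn trtp*avisitn / ddfm=kenwardroger".

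Of the primary model, SAP Section 8.3.3.1 says: "The model will include baseline SDMT score as a continuous explanatory variable". The tipping-point macro in the same appendix uses "var trtp y1 y2 y3".

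Under SAP Section 8.3.3.2 the sensitivity analyses run if more than 5% of either arm lacks the primary endpoint. A discussion in the study report is required "If any of the sensitivity analyses yields a result that is in a different direction from the result of the primary analysis". SAP Section 8.3.3.3 adds a forest plot of the SDMT "score using primary analysis, sensitivity analyses (excluding tipping point analysis) and supportive analysis will be provided".

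**The concern.** Step 3 predicts missing scores from placebo regressions that ignore baseline, and the completed data then go into a model that adjusts for baseline. Because the raw score is imputed, baseline enters neither as a predictor nor through the outcome. If SAGE-718 participants who leave have unusual baselines given their Day 14 and Day 28 scores, their imputed values are systematically off.

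This looks like a slip. Step 3 keeps the five-slot minimum and maximum lists that fit Step 2's five variables, although it now has three, and no reason is given for dropping baseline.

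At stake is how a sensitivity analysis is read. Its estimate is plotted beside the primary one, and a difference between them should reflect the missing data, not a missing covariate.

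**Working it through.** **1. The plan's own figure.** SAP Section 5.2 gives a difference of 4, SD of change 7.3, two-sided alpha 0.05 and 90% power. The normal approximation is n = 2 x (1.960 + 1.282)^2 x 7.3^2 / 4^2 = 2 x 10.51 x 53.29 / 16 = 70 per arm. The exact t-test needs 71 (power 0.9001). Then 71 / 0.8 = 88.75, so 89 per arm and 178 in all. The plan's figures reproduce.

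**2. Inputs not in the documents (assumptions).**
- Between-person SD s = 6, 9 or 12, with equal correlation between visits. A change SD of 7.3 fixes the within-person variance at 7.3^2 / 2 = 26.6. So rho = s^2 / (s^2 + 26.6) = 0.575, 0.752, 0.844, and the raw SD is 7.9, 10.4, 13.1.
- 20% lack Day 84, half leaving after Day 14 and half after Day 28.
- Selective dropout has log-odds -1 per baseline SD, or -1 per 7.3 points of change.

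**3. Where the error comes from.** With exchangeable correlation, the placebo regression of a later score on base and y1 weights each by rho/(1+rho). On base, y1 and y2, each weight is rho/(1+2rho). At s = 9 the baseline weight is 0.429 after Day 14 and 0.300 after Day 28, so baseline still predicts Day 84. Without base, the imputed value misses by minus that weight times (base minus its prediction from y1, or from y1 and y2). Dropouts with low baselines are imputed too high. Dropouts with poor early change have high baselines for their y1 and are imputed too low. In a first-order autoregressive series baseline has zero weight once a later score is known, so nothing is lost.

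**4. Hand check, no effect, s = 9, only SAGE-718 dropout baseline-related.** Integrating the logistic dropout curve over a normal baseline at 20% dropout puts the dropouts' mean baseline at -0.69 SD, or -0.69 x 10.4 = -7.2 points.
- After Day 14: residual -7.2 x (1 - 0.752^2) = -3.1; error 0.429 x 3.1 = 1.34; times 10% = 0.13.
- After Day 28: residual -7.2 x (1 - 2 x 0.752^2 / 1.752) = -2.5; error 0.300 x 2.5 = 0.76; times 10% = 0.08.
- Total: about +0.21.

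**5. Simulation, no effect** (2,000 trials per setting, 71 per arm, 20 imputations; ranges over s; shift = without minus with base; with base, the estimate stays within 0.02 of the primary one).

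| Dropout in SAGE-718 only | 20% missing | 10% missing | Half the log-odds |
|---|---|---|---|
| Low baseline | +0.20 to +0.24 | +0.12 to +0.14 | +0.10 to +0.14 |
| Poor change | -0.25 to -0.36 | -0.15 to -0.20 | -0.13 to -0.19 |

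Separate large-sample runs agree: +0.22 to +0.25 and -0.23 to -0.34 without base, within 0.04 of zero with it.

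**6. Where the bias disappears under no effect.** When both arms share the dependence, or dropout follows the Day 14 level, the with/without-base difference is 0.01 or less. Random dropout gives a shift within 0.01 of zero. A purely autoregressive series gives about zero. If half the between-person variance is autoregressive (rho 0.9, s = 9), the shifts are +0.13 and -0.19.

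**7. True effect of 4 from Day 14, random dropout.** Dropouts carry forward 4 times the summed weights on their on-treatment scores.
- With base, s = 9: 0.8 x 4 + 0.1 x 4 x 0.429 + 0.1 x 4 x 0.601 = 3.61.
- Without base: 0.8 x 4 + 0.1 x 4 x 0.752 + 0.1 x 4 x 0.859 = 3.84.
- For s = 6, 9, 12: 3.56, 3.61, 3.63 with base; 3.72, 3.84, 3.90 without. Simulation: 3.52, 3.59, 3.62 and 3.69, 3.82, 3.90.

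**8. Scale.** The unadjusted standard error at 71 per arm is 7.3 x sqrt(2/71) = 1.23. The largest shift in step 5 is 0.36 / 1.23 = 0.29 standard errors.

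**The case against.** Five points deserve weight.

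- **Selective SAGE-718 dropout alone is not enough.** A reader might infer that any dependence of SAGE-718 dropout on baseline or early change biases the estimate. It does not under no effect when placebo dropout has the same dependence, because placebo dropouts are imputed from the same regression and the errors cancel. The documents do not say how dropout will behave or how visits correlate. This stands and limits the claim.
- **The code is headed as sample code.** It holds placeholders and visible typing errors, and the evident intent includes baseline. That makes this a correction rather than a dispute over method. But the SAP text names no covariates, so nothing else tells the programmer to put baseline back.
- **The milder stress test is tempting to call bias.** In step 7 the estimate without baseline sits closer to 4. That is a different assumption about what dropouts retain, not an error against a known truth.
- **Frequencies of changed conclusions are illustrative only.** Under no effect with the selective dropout above, estimates of opposite sign to the primary one rose from 4 to 6% of trials with baseline to 10 to 14% without; at an effect of 4 they were at most 0.2% and 0.6%. These runs removed 20% from 71, a number already net of 20% dropout. That leaves about 57 of 89 with Day 84 data, a 36% loss. The mean shifts do not depend on this; the frequencies, and any rate of changed significance, do.
- **Missingness may be lower.** SAP Section 5.1 asks participants who stop treatment to keep attending.

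**Conclusion.** The omission is certain; its consequence is conditional and small. Under no effect, bias needs dropout that depends on baseline or early change differently between arms, and baseline that predicts Day 84 beyond Days 14 and 28. On the stated assumptions it is then about +0.2 or -0.2 to -0.4 points against a design difference of 4. Its direction depends on who leaves, so the analysis cannot be called conservative.

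A reader might go on to doubt the primary result. The documents give no ground for that: the primary model includes baseline, and neither it nor the testing sequence uses this code.

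Two neighbouring mismatches are separate and add no weight to this point. Step 3 requests m imputations within each of the m datasets from Step 2, while Section 8.3.3.2.2 analyses and pools m. The tipping-point macro applies its shift to placebo, while Section 8.3.3.2.3 shifts SAGE-718 values. No size is claimed for either. The correction should be made before database lock.

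**What to change.** - In Step 3, use `var base y1 y2 y3;` with four-slot minimum and maximum lists.
- In Step 3, set `nimpute=1`, so that m datasets are analysed and pooled as the text says.
- In Section 8.3.3.2.2, name baseline SDMT as an imputation covariate.
- In the tipping-point macro, add `base` to the variable list.
- As a separate correction, change that macro's `adjustobs` option so that the shift applies to SAGE-718 values, as Section 8.3.3.2.3 states. Adding baseline alone does not repair the macro.

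The cost is six small code edits and one sentence of text. Baseline SDMT is already in the dataset, and no new data or change to the primary analysis is needed.

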## 5.2. Sample Size and Study Power

The study is designed to detect a difference between placebo and the SAGE-718 group in the change from baseline to Day 84 for the primary endpoint, SDMT score. Using a 2-sided test at an alpha level of 0.05, a sample size of approximately 71 evaluable participants per treatment group would provide 90% power to detect a difference of 4 points between SAGE-718 and placebo arms in the change from baseline to Day 84 in SDMT values, assuming that the SD of the change from baseline in SDMT is 7.3 points.

Assuming a 20% dropout and a 1:1 randomization ratio, approximately 178 randomized participants (89 per treatment group) will be required to obtain 71 evaluable participants per treatment group. Evaluable participants are defined as those randomized participants who receive IP and have a valid baseline and at least 1 postbaseline SDMT assessment.

Additional participants may be randomized to ensure a sufficient number of evaluable participants or if the dropout rate is higher than 20%.

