##### Step 4. Convert datasets into long format in which CHG variable represents all change from baseline with different values of avisit.

##### Step 5. Conducting model-based analysis using each imputed dataset

The  $m$  complete datasets are analyzed using MMRM.

Step 6. Pooling the results from the imputed  $m$  datasets for inference

The results from the  $m$  complete datasets are combined to produce inferential results.

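### SAP Appendix B, control-based imputation: once the sample code is made to run, Step 6 pools three different contrasts under Day 84 instead of the single SAGE-718 versus placebo difference at Day 84

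*SAP*

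**What the plan says.** SAP 8.3.3.1 makes SAGE-718 versus placebo at Day 84 the primary comparison. SAP 8.3.3.3 asks for a forest plot of the Day 84 LS-mean difference in SDMT change from the primary, supportive and sensitivity analyses, leaving out only the tipping-point analysis. The control-based analysis (SAP 8.3.3.2.2) must therefore deliver that same Day 84 difference. On pooling, its text says only that the results from the m "complete datasets are combined to produce inferential results"; it names no contrast.

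The sample code in Appendix B does the following:

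- **Step 3** reads the Step 2 output, which already holds m data sets, and runs within `_imputation_` with "proc mi data=mono seed=xxx n impute=m outs=imputed".
- **Step 5** fits the MMRM with `trtp` and `avisitn` and requests "lsmeans trtp*avisitn / diff=all cl alpha=0.05".
- **Step 6** sorts the differences with the key "by avisit _imputatoin" (trailing underscore omitted here) and runs PROC MIANALYZE by `avisit`. It has no WHERE statement, no condition on the second visit of each pair, and no treatment key.

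**The concern.** A difference between two treatment-by-visit cells is identified by two arms and two visits. One visit label cannot identify it. The LS-mean block in Step 6 is keyed by treatment and visit, which does pick out one cell; the difference block has no equivalent.

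PROC MIANALYZE treats every row in a BY group as another imputation of the same quantity. Different contrasts in one group are averaged, and the spread between them is counted as between-imputation variance. Both the estimate and the standard error are then wrong for the intended comparison.

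The analysis will probably be run. SAP 8.3.3.2 triggers it when more than 5% of an arm lacks usable primary data, and SAP 5.2 assumes 20% dropout. The tipping-point analysis runs only after a significant primary result, so this is the one missing-not-at-random analysis that does not depend on significance. SAP 8.3.3.2 also requires the CSR to explain any sensitivity result in a different direction from the primary one. A pooling artefact could distort that comparison.

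**Working it through.** **Design figures.** SAP 5.2 states: "Using a 2-sided test at an alpha level of 0.05", "approximately 71 evaluable participants per treatment group would provide 90% power to detect a difference of 4 points", "assuming that the SD of the change from baseline in SDMT is 7.3 points".

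- Normal approximation: n = 2 × (1.960 + 1.282)² × 7.3² / 4² = 70 per arm.
- Noncentral-t power at 71 per arm: 0.9001.
- 71 / 0.8 = 88.75, so 89 per arm and 178 in total, as stated ("Assuming a 20% dropout and a 1:1 randomization ratio, approximately 178 randomized participants (89 per treatment group").

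The plan's figures are reproduced.

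**Does the printed code run?** Step 5 uses `avisitn` and `trtp`. Step 6 uses `avisit`, `treatment` and a misspelled `_imputatoin_`, none of which match, so it stops with an error. The PARMS= call with a model effect named `estimate` probably also has to become DATA= with a STDERR statement. What follows assumes only these repairs.

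**Which rows fall under Day 84?** The code comments give three visits: Days 14, 28 and 84. Two arms × three visits = 6 cells, and 6 × 5 / 2 = 15 differences per imputed data set. SAS placing the reference level (placebo) last is software behaviour that the documents do not state. On that basis the cell order is SAGE-718 Days 14, 28, 84, then placebo Days 14, 28, 84.

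| First-listed visit | Rows per imputation |
|---|---|
| Day 14 | 7 |
| Day 28 | 5 |
| Day 84 | 3 |

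The Day 84 rows are SAGE-718 Day 84 minus placebo Day 14, minus placebo Day 28 and minus placebo Day 84. Only the last is wanted. If placebo is ordered first, the group still has three rows, but they are placebo Day 84 minus SAGE-718 at Days 14, 28 and 84: another mixture, with the sign reversed.

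**Bias, reference level last.** Let P14, P28 and P84 be the mean placebo changes.

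Pooled value = Day 84 difference + [P84 − (P14 + P28 + P84)/3]

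The placebo profiles below are assumptions. The true difference is set to 4.0. The correct SE is 7.3 × √(2/71) = 1.225. The three-row SE is √(W + (1 + 1/(3m)) × B), with W = 1.225², m = 100, and B the variance across the 3m rows. The calculation leaves out real imputation noise.

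| Assumed P14/P28/P84 | Bias | Pooled value | SE, one row | SE, three rows |
|---|---|---|---|---|
| 0/0/0 or 2/2/2 | 0 | 4.0 | 1.225 | 1.225 |
| 1.0/1.5/2.0 | 2.0 − 1.5 = +0.5 | 4.5 | 1.225 | 1.292 |
| 0/−0.5/−1.0 | −1.0 + 0.5 = −0.5 | 3.5 | 1.225 | 1.292 |
| 1/2/3 | 3 − 2 = +1.0 | 5.0 | 1.225 | 1.474 |
| 0/−1/−2 | −2 + 1 = −1.0 | 3.0 | 1.225 | 1.474 |

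**Small simulation.** Assumptions: 400 runs per scenario, 89 per arm, SD 7.3, correlation 0.5, 20% missing at Day 84, control-based imputation with 20 imputations, an effect growing to 4 points at Day 84, and a 1.96 cut-off.

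| Assumed placebo profile | Rejection, correct pooling | Rejection, three-row pooling |
|---|---|---|
| 0/0/0 | 0.87 | 0.8575 |
| 1/2/3 | 0.88 | 0.94 |
| 0/−1/−2 | 0.885 | 0.305 |

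With no effect, rejection stayed between 0.02 and 0.0375 in every scenario under either pooling, because the larger SE offsets the shift. Even with a flat profile the average SE rose from 1.18 to 1.25 (effect 4), since observed placebo means differ between visits by chance.

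**Number of imputations.** Step 2 produces m data sets. Step 3 requests m more within each, which is m × m. SAP 8.3.3.2.2 speaks of m complete data sets and cites a range of 5 to 100. At m = 5 the printed request is 25; at m = 100 it is 10,000.

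**The case against.** The strongest reply is that this is labelled sample code. It contains placeholders for the seed, bounds and m, and Step 4 is given only in words. The SAP text fixes the target as the Day 84 between-arm difference, and no sentence asks for cross-visit contrasts. The primary MMRM sample code also requests all differences without a filter. A programmer who follows the text would select the right row.

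Part of this stands. The intention is clear, and in the primary model the request is harmless because the right row can be read from the output. The control-based code differs in that the pooling step merges the rows before anyone can choose among them. The pooling text names no contrast against which to check the result.

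A reader might also infer more than the documents support:

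- **That the printed code yields a specific biased number.** It does not run; the error appears only after repair.
- **That the comparison is always with averaged placebo.** That depends on the reference level being ordered last.
- **That the bias is about an eighth of the design effect (0.5 / 4).** This rests on an assumed practice gain. Protocol 11.2.1 describes the SDMT as little prone to practice effects, and SAP 8.3.1.1 schedules it at Screening and Day -1 before treatment.
- **That several copies of each participant enter the Step 5 model.** This depends on how the software handles the repeated index and was not tested. Only the mismatch between m and m × m is established.
- **That m should be fixed at 100.** SAP 8.3.3.2.2 sets m from the amount of missing information before the last patient's last visit, which is a legitimate choice.

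**Conclusion.** The code is wrong as written, within narrow limits. It does not run as printed. If only names and input syntax are repaired, the Day 84 group pools three contrasts per imputation, and neither its estimate nor its standard error belongs to the Day 84 SAGE-718 versus placebo difference.

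The size cannot be fixed from the documents. With the reference level last, the bias is zero when mean placebo change is equal at all three visits, and takes either sign otherwise (±0.5 points under the two milder profiles above). Separately, the imputation count in Step 3 disagrees with the text.

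A reader might take this as a threat to the primary result. It is not: the primary MMRM has no pooling step, and neither it nor the testing hierarchy uses this code. What is affected is the control-based sensitivity analysis, with its forest-plot entry and any CSR discussion that follows from it.

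**What to change.** - Make the Step 6 names match Step 5 (`avisitn`, `trtp`, `_imputation_`). Check the MIANALYZE input and, if needed, use DATA= with a STDERR statement.
- Before pooling, keep only rows where `avisitn` and `_avisitn` are both Day 84 and `trtp` differs from `_trtp`. Alternatively, request the single Day 84 contrast with an ESTIMATE or LSMESTIMATE statement. Pool one row per imputation with its standard error, and confirm that the sign is SAGE-718 minus placebo.
- Set NIMPUTE=1 in Step 3 within BY `_imputation_`, so that m data sets result, as the text says.
- Add to the pooling step in SAP 8.3.3.2.2 that the pooled quantity is the Day 84 SAGE-718 minus placebo difference.

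The cost is a few lines of sample code and one sentence of text. No new data are needed and the primary analysis does not change.
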